**CLINICAL TRIAL MASTER PROTOCOL AND INVESTIGATIONAL BROCHURE INFORMATION \***

	Master Protocol Investigator Brochure: <Specify Drug/Device>	Investigator Brochure: <Specify Drug/Device>	Sponsor Consent Form Template(s)
Version #:			
Version Date:			
[ X ] This study is investigator-authored (investigator developed the study and is conducting the study at UCI and/or with other non-UCI sites).			

\* Add columns as applicable

**NON-TECHNICAL SUMMARY**

Provide a brief non-technical summary or synopsis of the study that can be understood by IRB members with varied research backgrounds, including non-scientists and non-affiliated members.
The purpose of this study is to obtain information (such as lesion depth, depth of the most superficial part of the lesion, and the size and density of blood vessels) with the assistance of an imaging device, and use this information to assist in selection of laser settings for the treatment of skin conditions. The imaging modality is called Optical Coherence Tomography (OCT). Multiple laser modalities will be used including intense pulsed light (BroadBand Light, Profractional Sciton), pulsed dye laser (Vbeam Perfecta, Candela), long-pulse 755nm (GentleLASE, Candela), Sciton long-pulse 1064nm lasers, and non-ablative and ablative fractional resurfacing (Profractional, Sciton) lasers. All of the lasers noted above are the only ones that will be used in this study; they have 510k clearance and are being used as per their approved indications in this study. The choice of laser type is based on the skin lesion and is recommended by the physician, and subjects who are going to enroll in this study will already be planned to undergo laser treatment as a standard of care for their condition. This is a pilot study that will explore the utility of skin imaging in guiding the laser treatment of skin lesions.

## **SECTION 1: PURPOSE AND BACKGROUND OF THE RESEARCH**

Provide the scientific or scholarly rationale for the research. Describe the relevant background information and the specific gaps in current knowledge that this study intends to address.

The purpose of this research is to assist laser treatment of skin conditions by imaging the skin to obtain information about lesional skin. This is a pilot study that will explore the utility of skin imaging in guiding the laser treatment of skin lesions. This study will utilize Optical Coherence Tomography (OCT). Data acquisition of the skin will guide laser treatment by providing information on skin lesion characteristics.

There have been shown to be many applications for OCT. This imaging modality have been used to examine normal skin, burn scars, hemangiomas, nevus flammeus, fibrosarcomas, rosacea, and telangiectasias. Skin conditions to be studied include vascular lesions, scars, and inflammatory conditions. Normal and lesional skin will be assessed.

Currently, laser settings are selected without the assistance of imaging. Imaging with OCT provides more information about the characteristics of the skin lesion (such as lesion depth, depth of the most superficial part of the lesion, and the size and density of blood vessels), which could allow for more informed selection of laser settings to treat individual skin lesions. OCT has been used to examine laser treatments as well, but our proposed protocol would include the use of OCT to examine the stated skin lesions above before and after laser treatment in order to compare to prospective controls that did not undergo OCT imaging. The goal of our study is to optimize laser treatment with the assistance of OCT and guide future laser treatments. It has been shown that very early treatment of vascular lesions such as Port-Wine birthmark during infancy most often results in a better chance of lesion regression and can greatly improve the clinical and psychosocial well-being of the patient. Therefore, we will utilize OCT imaging, which is FDA-cleared for use on subjects of all ages to image our patient population.

The following imaging modalities will be used:

### **1) Optical Coherence Tomography (OCT):**

OCT is an imaging modality that uses light to image turbid media such as living tissues, and has been successfully used to generate high resolution (~10 micron) cross-sectional images of tissue microstructure in the human retina, skin, gastrointestinal tract, and genitourinary tract. OCT systems are now commercially available for ophthalmic and dermatologic use, and several clinical reports on the use of OCT in the vascular system and aero digestive tract (HS#2003-3025), Ophthalmology (HS#2004-3555), Pleural disorder (HS#2006-4982), Neural tissue (HS#2005-4775), Aneurysm healing (HS#2006-5031) and Oral Pathology (HS#2002-2805). This device focuses low power non-laser broad band infrared light onto tissue and does not involve input of significant amounts of energy into the subject; no temperature rise occurs. Because the wavelength of light used for imaging does not have adverse tissue effects, there is no risk.

Imaging with OCT provides information about the characteristics of the skin lesion (such as lesion depth, depth of the most superficial part of the lesion, and the size and density of blood vessels). OCT poses no known risks to the patients.

A multitude of studies have been conducted that validate the utility of OCT in imaging many types of skin lesions. Vascular lesions formulate a good portion of skin diseases studied by OCT, which includes rosacea, port-wine stain, hemangiomas, fibrosarcomas, cherry angiomas, and

telangiectasias. Other studies have examined imaging of burn scars, the micro-circulation of the skin, and vascular changes with topical medical application. In all of these studies, OCT imaging aided treatment, as well as provided a method to assess treatment outcome.

For port-wine stains, OCT has provided information such as vessel diameter and depth, which was discovered to be quite variable in PWS, indicating that tailored laser treatments are likely to improve result. Byers et al. noted that OCT was a robust, and non-invasive method for observing longitudinal dynamics of the subcutaneous microcirculation of tumors. Telangiectasias are a prominent feature of rosacea, and OCT has elucidated information about their treatment with intense-pulsed light to simply examine the effect of the treatment on the targeted lesions.

Provide relevant preliminary data (animal and/or human).

Multiple centers in the US and Europe have started using OCT to provide information about the skin. The PI participated in one study where information was gathered.

This information is not yet being used commonly to guide laser treatments.

Describe the purpose, specific aims or objectives. Specify the hypotheses or research questions to be studied.

The purpose of this research is to assist laser treatment of skin conditions by imaging the skin to obtain information about lesional skin. This is a pilot study that will explore the utility of skin imaging in guiding the laser treatment of skin lesions. The current standard of laser treatment without the assistance of imaging is to treat patients based on qualitative, visual characteristics of the skin lesion, such as vascularity, pliability, height, and pigmentation of the lesion. Imaging with OCT provides more information about the characteristics of the skin lesion (such as lesion depth, depth of the most superficial part of the lesion, and the size and density of blood vessels), allowing for more precise adjustment of laser settings to treat individual skin lesions. Laser treatment will be used within the approved normal parameters consistent with the standard of care. Our hypothesis is that treatments with the assistance of the OCT device will exhibit improvement of their lesions with few side effects.

Describe the primary outcome variable(s), secondary outcome variables, and predictors and/or comparison groups as appropriate for the stated study objectives/specific aims.

Primary outcome variables include assessment of photograph improvement. Two board certified dermatologists will grade the degree of improvement (clearance of the lesion) in quartiles (no clearance=0-25, mild clearance=26-50, good clearance=51-75, excellent clearance=76-95, complete clearance=96-100).

Secondary outcome variables: repeat measurements with OCT, including lesion thickness, size, size of blood vessels, and density of blood vessels, and number of superficial blood vessels.

List up to ten relevant references/articles to support the rationale for the research. Do not append an extensive NIH-grant-style bibliography.

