### **2. Study Design**

Include an explanation of the study design (e.g., randomized placebo-controlled, cross-over, cross-sectional, longitudinal, etc.) and, if appropriate, describe stratification/ randomization/blinding scheme.

This is a longitudinal study with matched prospective controls. The patients will undergo treatment and follow-up over the course of 1-7 months. Their results will be compared to that of matched prospective controls with similar treatment and follow duration. There is no placebo, and patients will not be blinded.

Patients will be stratified based on their lesion type and the size of the lesion as these factors may impact the response to laser treatment and thus the data measurements from OCT. Photographs of the patients' treated lesions will be rated for lesion improvement by blinded physicians. OCT measurements of the lesion of interest will be used to validate the improvement and cosmetic results.

Provide precise definitions of the study endpoints and criteria for evaluation; if the primary outcomes are derived from several measurements (i.e., composite variables) or if endpoints are based composite variables, then describe precisely how the composite variables are derived.

Primary endpoints include photographic improvement of the lesion(s) of interest after 1 or more laser treatments. Two board certified dermatologists grade the degree of improvement (clearance of the lesion) in quartiles (no clearance=0-25, mild clearance=26-50, good clearance=51-75, excellent clearance=76-95, complete clearance=96-100). It will be up to the experienced treating dermatologist to determine the number of treatments necessary for maximum clearance of the lesion(s).

Secondary endpoints include measurements with OCT, which show reduced lesion thickness, lesion size, size of blood vessels, and density of blood vessels, and number of superficial blood vessels.

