### 3. Research Procedures

Provide a detailed chronological description of all research procedures.

A screening log of all potential subjects will be kept at our site. All screening evaluations must be reviewed by the investigator to establish patient eligibility prior to registering the patient for this study.

The following screening evaluation should be completed for all subjects on the first visit:

- Informed consent and photograph release form
- Focused medical history including diagnosis of lesion if applicable. This includes general questioning about the patient's health, well-being, allergies, and medications, and history of the skin lesion in question as identified by the patient and confirmed by the physician.
- Focused skin exam. This includes a detailed medical examination of the skin lesion in question.
- Documentation of area of skin to be studied. This will be determined by the patient's indication and confirmed by the physician.

On visit number one of the study, patients will consent to the study, and an area of skin to be studied will be photographed by digital photography. If the study area is on the face, subjects will be offered to protect their identity.

Non-invasive imaging will then be performed with OCT. Each individual scan with OCT takes about 30 seconds to complete, and we may perform multiple scans on larger lesions. Based on the data and information obtained, the appropriate laser device and settings will be applied for the most optimal treatment to achieve the best results with the fewest side effects. Then laser treatment will be performed on the lesion of interest. Immediate post-treatment imaging and photography will be conducted to assess the results of the treatment. This first visit should take no more than 1.5 hours: approximately 20 minutes for a medical history and focused skin examination, 30 minutes for imaging including photographs, and 30 minutes for laser treatment. These times are all maximums and will likely be shorter. The patient may take as long as needed to consent and is permitted to take the consent form home and return another day to sign and enroll.

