Some subjects may be asked to participate in more than one imaging session. They will have the option of refusing participation in additional sessions. Follow-up examinations will be performed every 4 weeks. During these examinations, photography and imaging of the lesion of interest will be performed with optional laser treatments to be performed at the discretion of the treating physician and the patient. If no laser treatment is necessary, then the visit should take no more than 30 minutes for a quick follow-up and imaging. Additional laser treatment will require no more than 30 minutes to complete. The number of follow-ups is also determined at the discretion of the treating physician and the patient but could range from 1 to 6 depending on the response of the lesion to treatment.

Matched prospective controls will be gathered to be compared against the imaged, treated, experimental group. The prospective controls will be matched to age, gender, skin type, and type of skin lesion. They will be gathered via a retrospective chart review by abstracting and data directly from our own records.

Describe the duration of a subject's participation in the study. If there are sub-studies, include duration of participation in each sub-study.

For each visit: history and skin examination-30 minutes, imaging – up to 30 mins, and laser treatment – up to 30 mins. These are all maximums and will likely be shorter.

At a follow-up, the patient may or may not receive a laser treatment thus shortening the visit. A patient would be expected to have 1-6 follow ups depending on their response to treatment, so their maximum time in this study could range from about 1 to 6 months. Each follow-up visit is made about 4 weeks from the prior visit.

List data collection instruments (e.g., measures, questionnaires, interview questions, observational tool, etc.).

*Investigator-authored, non-standardized, or un-validated measures must be submitted for review.*

Standardized photography,  
OCT

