##### Statistical Analysis Plan

Primary Objective: The outcome of degree of improvement will be compared between those previous patients that were treated conventionally as a prospective control and those prospective patients who will be treated with assistance from the OCT device. We will use a two-sample t-test to examine the difference in degree of improvement between the two groups at each treatment.

Secondary Objective: We will present the mean/standard deviation and 95% confidence interval of all secondary outcomes (including lesion thickness, size, size of blood vessels, and density of blood vessels, and number of superficial blood vessels.) at each treatment.

2. Describe the primary statistical method(s) that will be used to analyze the primary outcome(s) or endpoints.

N/A

3. Describe the secondary statistical method(s) that will be used to analyze the secondary outcome(s) or endpoints.

N/A

4. If appropriate describe secondary or post hoc analyses of primary outcome(s) or other exploratory analysis.

N/A

5. Sample Size Determination: Explain how the overall target sample size was determined (e.g., power analysis; precision estimation), providing justification of the effect size for the primary outcome based on preliminary data, current knowledge/literature and/or cost consideration; if appropriate, provide sample size justification for secondary outcomes. Power analysis should (at least) match the primary outcome/endpoint.

Literature indicated that laser treatment of skin lesions yields varying degree of clearance across different types of lesions. For example, the Ashinoff et al. 1991 study showed 50% lesion clearance after 3 laser treatments for port wine birthmarks in 12 infants. Another Ashinoff et al. 1991 study showed 70% lesion clearance after 3 laser treatments for capillary hemangiomas in 10 infants. The Clark et al. 2002 study showed 50% lesion clearance after 3 laser treatments for rosacea in 12 adults. Last but not least, the Geronemus 1991 study showed 90% lesion clearance after 1 laser treatment for spider telangiectases in 12 adults. Based on these data, we calculated a mean of 65% ( $\pm 20\%$ ) lesion clearance after 3 laser treatments for any lesion type. Adjusting for the unique characteristics of our patient population at UCI, we estimated a mean lesion clearance of 40% ( $\pm 20\%$ ) after 1 laser treatment for any lesion type.

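### The hypothesis promises few side effects, but side effects are not a named outcome, a listed measure or part of the analysis

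*Combined protocol and SAP*

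**What the plan says.** Section 1 gives one hypothesis, that OCT-assisted treatments "will exhibit improvement of their lesions with few side effects". No threshold defines few, and no comparator is named for side effects. Section 6, Research Procedures, repeats the aim: the OCT data are used to choose the laser and settings "to achieve the best results with the fewest side effects".

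The outcomes are these:

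- **Primary:** "Primary outcome variables include assessment of photograph improvement", graded by two dermatologists as clearance.
- **Secondary:** Section 1 has "Secondary outcome variables: repeat measurements with OCT, including lesion thickness, size, size of blood vessels, and density of blood vessels", plus the number of superficial vessels. Section 6, Study Design, lists the same kind of measure: "Secondary endpoints include measurements with OCT, which show reduced lesion thickness, lesion size, size of blood vessels, and density of blood vessels".

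The data collection instruments in Research Procedures are "Standardized photography" and OCT. Follow-up visits every 4 weeks provide for photographs and imaging, with further laser treatment optional. For controls, the screening list in Section 3 has age, diagnosis, lesion location, clearance and treatment response.

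The Statistical Analysis Plan has a two-sample t-test on degree of improvement. For the rest it says "We will present the mean/standard deviation and 95% confidence interval of all secondary outcomes" and names the OCT measures. The items for further methods and exploratory analyses are answered N/A. The form's instruction at the head of Statistical Considerations is that the analysis should match the aims and hypotheses of Section 1.

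**The concern.** OCT guidance can change a patient's result only by changing the laser or its settings. A gain in clearance therefore has to be read together with what the changed settings did to the skin. The plan states an expectation about both sides of that balance and sets up measurement for only one.

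If the plan is followed as written, a report could say that OCT guidance improved clearance with few side effects when the second statement rests on no defined outcome, no common way of asking and no denominator. A side-effect cost of the OCT-guided settings could equally go unreported. Side effects that are not asked about at the visit are hard to recover reliably afterwards.

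**Working it through.** **1. Tracing the two parts of the hypothesis through the plan**

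| Where a measure would appear | Improvement | Side effects |
|---|---|---|
| Primary outcome (Section 1; Section 6, Study Design) | Photographic clearance grade | None |
| Secondary outcomes (same places) | OCT measures | None |
| Follow-up content (Research Procedures) | Photographs and imaging | None listed |
| Instruments (Research Procedures) | Photography, OCT | None |
| Control data items (Section 3, screening list) | Clearance, treatment response | None listed |
| Analysis (Statistical Analysis Plan) | t-test; mean, SD and 95% CI | None |

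Side effects appear in the procedures only as an aim when settings are chosen: "for the most optimal treatment to achieve the best results with the fewest side effects". The risk item in Section 7 points to the consent form, and it asks for foreseeable risks, not for an outcome.

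**2. What the sample size covers**

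Inputs from Statistical Considerations: mean clearance 60% against 40%, so a difference of 20 points; SD 20 points (reading the ± figure as an SD); two-sided 5%; 80% power.

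- Normal approximation: n per group = 2 × (1.960 + 0.842)² × (20/20)² = 15.7, so 16.
- Exact noncentral t: 16.7, so 17 per group, with power 80.7% at 17.

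The stated 17 per group reproduces. It concerns clearance only; there is no side-effect rate, margin or test to reproduce.

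**3. What recorded side effects could show**

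The enrolment table in Section 3 expects 17 OCT patients to complete and allows up to 30 to be consented, including withdrawals and screen failures. The number treated should therefore lie between about 17 and at most 30. Exact (Clopper-Pearson) two-sided 95% limits follow. For zero events the upper limit is 1 − 0.025^(1/n).

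| Patients with any side effect | n = 17 | n = 30 |
|---|---|---|
| 0 | 0 to 19.5% (1 − 0.025^(1/17)) | 0 to 11.6% (1 − 0.025^(1/30)) |
| 1 | 0.1% to 28.7% | 0.1% to 17.2% |
| 2 | 1.5% to 36.4% | 0.8% to 22.1% |

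**4. Whether the groups could be compared formally**

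The documents give no side-effect rates, so the following pairs are assumptions. With 17 per group, approximate two-sided 5% power is 12% for 20% against 10%, 30% for 30% against 10%, 53% for 40% against 10%, and 74% for 50% against 10%. Only a descriptive contrast is realistic.

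Steps 3 and 4 describe the precision of the remedy. The gap itself is established by step 1.

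**The case against.** The strongest case on the other side has four parts.

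- **Clinical data will exist.** The plan has imaging and photographs straight after treatment, time for history and skin examination at each visit, photographs every 4 weeks, and subjects who are patients in the medical record. Treatment response in control charts might include reactions. This stands: a reader might infer that nothing about side effects will be recorded, and the documents do not support that. The case report form and consent form are not among the documents reviewed, so absence from all data collection cannot be shown. What can be shown is that no listed outcome, instrument or analysis covers side effects. Photographs rated by blinded physicians for improvement are not a side-effect assessment.
- **Laser use stays within approved limits and usual care.** Section 1 says so just before the hypothesis. This also stands, and it bars the inference that the plan exposes patients to a demonstrated safety problem. It does not show that side effects were few, because OCT is meant to alter choices within those limits.
- **The phrase is a qualifier in a pilot.** The hypothesis that is powered and tested is 60% against 40% clearance. A reader might infer that the trial's main test fails; it does not. But the study being a pilot argues for descriptive reporting, not for leaving the outcome out.
- **The sample is too small to establish few.** This is largely true, and the limits above show it. It is a reason to word the conclusion by the interval or to drop the claim.

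**Conclusion.** The point holds as a mismatch between hypothesis and plan. The side-effect part of the Section 1 hypothesis has no named outcome, planned systematic recording or analysis behind it, so it cannot be supported as written. This falls short of the form's own instruction that the analysis should match the hypotheses. The primary clearance comparison and its sample size are unaffected.

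The conclusion rests on the outcome, procedure, instrument and analysis sections, all of which are present. It assumes that no separate case report form, unavailable here, already sets up a side-effect measure. If one does, the outcome list and analysis plan would still need to name it.

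An added outcome could support a descriptive rate only: zero events would leave an upper 95% limit between about 11.6% (all 30 treated) and 19.5% (17 treated). The change is worth making before data collection, but the study does not depend on it.

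**What to change.** Add treatment side effects as a descriptive secondary outcome in Section 1, Study Design and the Statistical Analysis Plan:

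- **Record** presence or absence, type and severity, with brief definitions, at the existing assessment straight after treatment and at each existing 4-weekly visit.
- **Report** the number and proportion of all treated OCT patients with any side effect, with an exact 95% CI. Use everyone treated as the denominator, not completers only.
- **Show the number of treatments received alongside.** With 1 to 6 follow-ups and optional laser at each, a patient could have from 1 to 7 treatments (first visit plus up to 6), so exposure will differ.
- **Controls:** abstract the same item from their records, state how it was recorded, and present the contrast as descriptive only.
- **Conclusion:** limit any statement about few side effects to what the interval supports.

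If side effects will not be recorded, remove the phrase from the hypothesis.

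The cost is a short form section with agreed definitions at visits already planned, one extra item in the control abstraction, and one table. Treatment, sample size and primary analysis do not change. The downside is that Research Procedures has controls gathered by retrospective chart review, where side effects may be under-recorded. That would make the OCT group look worse by comparison and should be stated with the table.
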